1 PROTOCOL SYNOPSIS

Study Title	A Phase 3, Randomized, Single dose, Open-Label Study to Investigate the Safety and Efficacy of OTL38 Injection (OTL38) for Intra-operative Imaging of Folate Receptor Positive Ovarian Cancer
Sponsor	On Target Labs, Inc. [REDACTED]
Primary Objectives	
 To confirm the efficacy of OTL38 in combination with fluorescent light to detect additional Folate Receptor-positive (FR+) ovarian cancer lesions not detected by palpation and visualization under normal light in patients with FR+ ovarian cancer scheduled to undergo primary surgical cytoreduction, interval debulking, or recurrent ovarian cancer surgery
Secondary Objectives	
 To estimate the proportion of folate positive ovarian cancer patients in whom all lesions detected by fluorescent light only are histologically negative, the patient level False Positive Rate (FPRp) To estimate the Sensitivity and False Positive Rate for OTL38 in combination with fluorescent light with respect to the detection of FR+ ovarian cancer lesions confirmed by [REDACTED] pathology To assess the safety of using OTL38 and [REDACTED] Imaging System or Quest Spectrum Imaging System for intraoperative imaging [REDACTED]
Exploratory Objectives	
 To estimate the lesion inoperability rate for all lesions identified by fluorescent light only. To describe the diagnostic characteristics of OTL38 in combination with fluorescent light for lesions of various histological and pathological cell types To assess CA-125 levels before and after surgery To estimate the plasma pharmacokinetics (PK) of OTL38 in patients with FR+ ovarian cancer scheduled to undergo primary surgical cytoreduction, [REDACTED]
Study Design	
This is a phase 3, randomized, multi-center, single dose, open label, pivotal study in patients diagnosed with, or with high clinical suspicion of, ovarian cancer scheduled to undergo primary surgical cytoreduction, interval debulking, or recurrent ovarian cancer surgery.
 
[REDACTED]

	
[REDACTED]
 
[REDACTED]
 
Efficacy will be assessed for patients undergoing both normal light and fluorescent light imaging. All patients exposed to OTL38, [REDACTED] will be followed for safety. The study will consist of a screening period of up to 28 days prior to the scheduled surgery, a diagnosis and treatment period (day of surgery; Day 1), and safety assessment visits on Day 7 (+/-4) and Day 28 (+/-4) after surgery. The study database will be frozen when the last patient completes the Day 28 assessment (which will be considered the study completion date); AEs/ADEs judged by the Investigator to be at least possibly related to study drug will continue to be reported regardless of how much time has elapsed since the last exposure to study drug. [REDACTED]

Treatment	
• OTL38 is a folate analog ligand conjugated with an indole cyanine-like green dye.• Each patient will complete a single dose of 0.025 mg/kg OTL38 at least 1 hour before the initiation of fluorescent imaging.• The imaging systems [REDACTED] that will be used for the intraoperative visualization of ovarian cancer labeled with OTL38 are not yet approved for use with OTL38, and therefore are considered investigational for purposes of this study.
Study Duration	
Patients will complete a single dose of 0.025 mg/kg OTL38 at least 1 hour hours before the initiation of fluorescent imaging. Safety assessments will occur on Day 7 (\pm 4) and Day 28 (\pm 4). [REDACTED] levels will be measured at a long-term follow-up visit [REDACTED] after surgery. [REDACTED]


Eligibility Criteria
	
Inclusion:
 
 1. Female patients 18 years of age and older 2. Have a primary diagnosis, or at high clinical suspicion, of primary ovarian cancer (of epithelial type), planned for primary surgical cytoreduction, interval debulking, or have recurrent ovarian cancer surgery, and: 
 o Who are scheduled to undergo laparotomy for the debulking surgery OR o Who are scheduled to undergo laparoscopy and pre-authorized to undergo laparotomy for the debulking surgery if cancer is detected on the laparoscopy 3. A negative serum pregnancy test at Screening followed by a negative urine pregnancy test on the day of surgery or day of admission for female patients of childbearing potential 4. Female patients of childbearing potential or less than 2 years postmenopausal agree to use an acceptable form of contraception from the time of signing informed consent until 30 days after study completion 5. Ability to understand the requirements of the study, provide written informed consent for participation in the study and authorization of use and disclosure of protected health information, and agree to abide by the study restrictions and to return for the required assessments 
Exclusion:
 
 1. Previous exposure to OTL38 2. Known FR-negative ovarian cancer 3. Planned surgical debulking via laparoscopy or robotic surgery, with no intent of laparotomy. 4. Patients with known ovarian cancer miliary disease determined pre-operatively to be inoperable. 5. Any medical condition that, in the opinion of the investigators, could potentially jeopardize the safety of the patient 6. History of anaphylactic reactions 7. History of allergy to any of the components of OTL38, including folic acid 8. Pregnancy or positive pregnancy test 9. Clinically significant abnormalities on electrocardiogram (ECG) 10. Presence of any psychological, familial, sociological or geographical condition potentially hampering compliance with the study protocol and follow-up schedule 11. Impaired renal function defined as eGFR < 50 mL/min/1.73m² 12. Impaired liver function defined as values > 3x the upper limit of normal (ULN) for alanine aminotransferase (ALT), aspartate aminotransferase (AST), alkaline phosphatase (ALP), or total bilirubin. 13. Known Stage IV ovarian cancer with brain metastases 14. Received an investigational agent in another clinical trial within 30 days prior to surgery 15. Known sensitivity to fluorescent light
------------------------------------	--

Number of Subjects
	
A minimum sample size of 100 evaluable patients is required to evaluate the primary efficacy endpoint. [REDACTED]

Number of Investigator Sites
	
Up to 16 investigational sites (14 in the United States and 2 ex-U.S. [the Netherlands]).

Assessments
	
At specified time points as outlined in the schedule of events, patients will undergo the following procedures: collection of informed consent, medical history, demographics, physical exam including weight, vital signs including temperature, and ECG. Patients will also provide samples for clinical chemistry, CBC with differential, and a serum/urine test for women of child-bearing potential. Concomitant medications and adverse events as reported by the patient will be monitored.
 
Blood samples for PK analysis will be drawn from all subjects at sparse time points (30, 60 and 90 minutes) following the start of OTL38 infusion (see Section 6.5).
 
[REDACTED]

Study Endpoints
	
Primary Efficacy:
 
 Proportion of patients with at least one evaluable FR+ ovarian cancer lesion confirmed by [REDACTED] that was detected using the combination of OTL38 and fluorescent light but not under normal light or palpation. [REDACTED] 
[REDACTED]

	
Secondary Efficacy:
 
• False Positive Rate at the patient level (FPRp) [REDACTED]• Sensitivity or True Positive Rate (TPR) for OTL38 in combination with fluorescent light. [REDACTED]• False positive rate (FPR) for OTL38 in combination with fluorescent light, for the purpose of this protocol. [REDACTED] 
[REDACTED]
 
[REDACTED]
 

[REDACTED]	[REDACTED]	[REDACTED]	

[REDACTED]	[REDACTED]	[REDACTED]	

 
[REDACTED]
	[REDACTED]	[REDACTED]	[REDACTED]	[REDACTED]	[REDACTED]	[REDACTED]
[REDACTED]	[REDACTED]	[REDACTED]					
[REDACTED]	[REDACTED]	[REDACTED]					
	
[REDACTED]
 
[REDACTED]
 
[REDACTED]
 
[REDACTED]
						

	
█ [REDACTED]█ [REDACTED]█ [REDACTED]█ [REDACTED]█ [REDACTED]█ [REDACTED]█ [REDACTED] to evaluable lesion status for:
- Cancer (ovarian or other cell type) that are FR+- Cytologically abnormal lesions that are FR+• Proportion of patients in whom the Pre-Fluorescence Surgical Plan was changed based on fluorescent imaging both prior to initiation of the surgical procedure and upon reimaging of the surgical field after the surgical procedure immediately prior to surgical closure.• CA-125 levels before and after surgery 
Safety:
 
• Incidence rates of treatment-emergent AEs (TEAEs), SAEs, and Adverse Device Effects (ADEs), and changes in clinical laboratory values, vital signs, physical examination, concomitant medications and ECG through Visit 4. 
Pharmacokinetics:
 
• Primary plasma pharmacokinetic (PK) parameters for OTL38, including systemic clearance (CL), volume of distribution of the central and peripheral compartments (V_c, V_p), and distributional clearance(s) (CL_d), on a population and individual patient level.• Effects of patient specific covariates (e.g. baseline demographics and laboratory value indicators of renal and hepatic function) upon PK parameters.
--	---

Statistical Methods	
Analysis of Primary Efficacy Endpoint
 
The primary analysis of the primary efficacy endpoint (Section 8.2.5.1) will be a one-sample test for a proportion via an exact binomial test conducted at the two-tailed alpha level of 0.05. [REDACTED]
 
Analysis of Secondary Efficacy Endpoints
 
The patient level False Positive Rate (FPR_p) will be analyzed descriptively, providing the point estimate and the two-sided 95% Wilson (score) confidence interval. [REDACTED]
 
[REDACTED]
 
[REDACTED]
 
[REDACTED]
 
[REDACTED]
 
Analysis of Safety
 
For all safety assessments, the baseline value will be the last non-missing value recorded for a particular safety parameter before exposure to study drug. In general, the analysis of safety will be descriptive.
 
Sample Size Estimation
 
[REDACTED]
 
[REDACTED]
 
[REDACTED]

----------------------------	--

	
[Redacted content]

--	---------------------------

Table of Contents

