5.1.2 Safety assessment

All AEs deemed to be related to OTL38 and of severity graded as mild, moderate or severe will be monitored. The following definitions of severity will be considered in this determination:

- Mild: Awareness of signs or symptoms, but easily tolerated and are of minor irritant type. Symptoms do not require therapy or a medical evaluation; signs and symptoms are transient.
- Moderate: Events introduce a low level of inconvenience or concern to the participant, but are usually improved by simple therapeutic measures; moderate experiences may cause some interference with functioning.
- Severe: Events generally require systemic drug therapy or other treatment; they are usually incapacitating.

Safety assessments will also include changes in labs, vitals, and ECG.

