7.2.2 Laboratory Abnormalities

To the extent possible, all laboratory abnormalities observed during the course of the study will be included under a reported AE describing a clinical syndrome (e.g., elevated blood urea nitrogen and creatinine in the setting of an AE of “renal failure” or elevated ALT/AST in the setting of an AE of “hepatitis”). In these cases (e.g., an AE of renal failure), the laboratory abnormality itself (e.g., elevated creatinine) does not need to be recorded as an AE.

In the absence of a reported AE identifying a clinical syndrome that encompasses the observed laboratory abnormality that “isolated” laboratory abnormality itself should be reported as an AE.

Patients experiencing AEs or laboratory abnormalities will be assessed and appropriate evaluations and interventions performed until all parameters have returned to baseline levels, or are consistent with the patient’s then-current physical condition, in the opinion of the investigator.

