7 GENERAL ANALYSIS AND REPORTING CONVENTIONS

The following is a list of general analysis and reporting conventions to be applied for this study.

- Baseline will be defined as the last recorded non-missing observation prior to exposure to study drug.
- Categorical variables will be summarized using counts (n) and percentages (%) and will be presented in the form “n (xx.x)”. Percentages will be based on the relevant total category count excluding missing data if not otherwise mentioned. To ensure completeness, where relevant, summaries for categorical and discrete variables will include all categories, even if no patients had a response in a particular category.
- Continuous variables will be summarized using mean, SD, minimum, maximum, median, and number of patients. The mean and median will be reported to one more level of precision than the original observations, and the SD will be reported to 2 more levels of precision than the original observations. The minimum and maximum will be the same precision as the original data.
- For tests of hypotheses, the associated p-value and confidence interval (CI) will be reported, where applicable. All p-values will be rounded to 3 decimal places; p-values that round to “0.000” will be presented as “<0.001”.
- Dates will be displayed as ddmmmyyyy (e.g., 24Jan2005).
- Age (in years) will be calculated using the date of birth and the date of informed consent as (date of informed consent – date of birth) / 365.25.

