14.5 Clinical Laboratory Evaluations

The analysis of laboratory parameters will include descriptive statistics for the change from baseline to each post-baseline study visit as well as shifts from baseline to each post-baseline study visit for categorical lab parameters. In addition, shift tables (i.e., low-normal-high at baseline versus low-normal-high at last visit) will be provided. Urinalysis and pregnancy results will not be summarized but will be provided in a data listing. For all relevant laboratory data, values above or below normal limits will be flagged along with the direction of abnormality in line listings.

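### The laboratory shift table has only low, normal and high categories, so a patient admitted with a liver test above ULN (allowed up to 3x) cannot register an upward shift, however large the rise

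*Protocol*

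**What the plan says.** Exclusion 12 (protocol synopsis and section 5.2.2) covers "Impaired liver function defined as values > 3x the upper limit of normal (ULN) for alanine aminotransferase (ALT", and the sentence goes on to AST, ALP and total bilirubin. A patient above 1x and up to 3x ULN on any of these is therefore eligible.

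For the analysis, SAP 14.5 and protocol 8.2.6.2 use the same wording. Four outputs bear on numeric laboratory values:

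- A change summary: "descriptive statistics for the change from baseline to each post-baseline study visit". SAP section 7 fixes its content: "Continuous variables will be summarized using mean, SD, minimum, maximum, median, and number of patients".
- A shift table: "shift tables (i.e., low-normal-high at baseline versus low-normal-high at last visit) will be provided". The i.e. makes these three categories the definition, not an example.
- A by-visit shift output, but only "shifts from baseline to each post-baseline study visit for categorical lab parameters". Liver tests are numeric, and neither document defines grades or bands for them.
- Listings in which "values above or below normal limits will be flagged along with the direction of abnormality in line listings".

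There is also a route through adverse events. Under protocol 7.2.2, when no reported syndrome explains an abnormal result, the "laboratory abnormality itself should be reported as an AE". SAP 14.3 tabulates treatment-emergent events by preferred term, with the number and percent of patients in the safety set.

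**The concern.** The entry rule and the shift table do not fit together. The entry rule lets in patients who already occupy the top category, and the top category has no upper divisions. For these patients an upward shift is impossible by construction.

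Among patients who enter normal, the normal-to-high cell pools a value just over the limit with one many times over it. After debulking surgery both are plausible, and a reader of the table cannot tell them apart.

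This matters because changes in laboratory values are a safety endpoint (protocol 6.4, SAP 12.4) and SAP section 5 states that there is no comparator group. Each patient's own baseline is the main reference, and the shift table is the planned categorical comparison with it. A table with no upward shifts in the already-high group says nothing about whether those patients worsened.

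**Working it through.** The plan gives no figure to reproduce here. The check applies its three-category rule to illustrative values, then asks what the other outputs would show.

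**Inputs from the documents.** Entry limit: up to 3x ULN (Exclusion 12). Categories: low, normal, high, with high taken as above 1x ULN (SAP 14.5). Summary statistics: SAP section 7. Sample size: the synopsis gives a minimum of 100 evaluable patients; the readable text gives no size for the safety set.

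**Assumptions.** Safety set N = 120, range 100 to 150. Share entering above ULN on a liver test: 5% to 20%. All individual values below.

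**Step 1: classify example rises.** The fold rise is post-dose divided by baseline. The last two columns apply the counts proposed in the fix, with bands <=1, >1-3, >3-5, >5-10 and >10.

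| Baseline to post-dose (x ULN) | Fold rise | Planned table | Above 3x ULN and in a higher band | Multiple of baseline |
|---|---|---|---|---|
| 0.9 to 1.1 | 1.22 | normal to high: shift | no | below 2x |
| 0.95 to 1.05 | 1.11 | normal to high: shift | no | below 2x |
| 1.1 to 3 | 2.73 | high to high: none | no | >=2x |
| 1.5 to 5 | 3.33 | high to high: none | yes | >=3x |
| 2.5 to 10 | 4.00 | high to high: none | yes | >=3x |
| 3 to 3.1 | 1.03 | high to high: none | yes | below 2x |
| 3 to 9 | 3.00 | high to high: none | yes | >=3x |
| 3 to 20 | 6.67 | high to high: none | yes | >=3x |

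The planned table counts the 1.11-fold and 1.22-fold rises and misses every rise of 2.7-fold or more. The 1.1 to 3 and 3 to 3.1 rows show why the fix needs both counts.

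**Step 2: what the change summary would show.** If k patients each rise by d and the rest do not change, the mean change is k x d / N. With k = 3 and d = 10 - 2.5 = 7.5x ULN:

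- N = 100: 22.5/100 = 0.225
- N = 120: 22.5/120 = 0.188
- N = 150: 22.5/150 = 0.150

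At N = 120 the SD of change is the square root of (3 x 7.5² - 120 x 0.1875²)/119 = (168.75 - 4.22)/119 = 1.38, so SD = 1.18x ULN. The maximum is 7.5x ULN. With a single patient rising from 3x to 9x ULN, the mean change is 6/100 = 0.06 or 6/150 = 0.04, and the maximum is 6x ULN.

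So the mean hardly moves, while the SD and maximum do react. The maximum shows that one large rise occurred, but not how many there were or from what baseline.

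**Step 3: what a banded table would show.** In the same scenario it gives 3/120 = 2.5% (exact 95% CI 0.5% to 7.1%), where the planned table gives 0 upward shifts.

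**Step 4: how many patients could be affected.** 0.05 x 120 = 6 to 0.20 x 120 = 24 patients would enter already high on a liver test, under the assumed share.

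**The case against.** The strongest reply is that the information is reported elsewhere, and with a rate. An isolated abnormality is an adverse event under protocol 7.2.2, and SAP 14.3 gives the percent of patients by preferred term. The change summary reports SD and maximum at each visit, and the listings carry every value. This stands: a reader might infer that a rise from a high baseline vanishes from the safety report, and the documents do not support that. What remains is narrower. Section 7.2.2 sets no numeric threshold and has no rule for worsening from an already abnormal baseline, so whether such a rise is reported depends on the investigator. The preferred-term rate does not separate small rises from large ones, and the listing flag gives direction only.

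A reader might also infer that a large rise without symptoms would be graded mild, because severity rests on symptoms, therapy and functioning. That goes too far. The definition of mild says "Symptoms do not require therapy or a medical evaluation; signs and symptoms are transient", and 7.2.2 calls for patients with laboratory abnormalities to be evaluated, so a marked rise fits mild poorly. Even a mild event stays in the preferred-term table.

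Two more points are fair. Every patient is expected to receive the drug and have surgery, so a banded rate could not attribute a rise to the drug; it would only describe what happened. And SAP section 1 places draft tables in a separate document that was not available, so bands may exist there. The SAP wording would still define the table as low-normal-high.

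**Conclusion.** The point holds as a gap in descriptive safety reporting. For a patient above ULN at entry, an upward shift in the planned table is impossible; this follows from the text and needs no assumption. No other planned output counts patients by size of rise.

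Its practical size is unknown. The documents do not give the share entering above ULN or the size of the safety set, and the figures of 6 to 24 patients and 3/120 rest on the assumptions stated above. The readable text reports no hepatic signal, although part of the risk section is redacted.

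Two wider readings should be avoided. The endpoint is laboratory values in general; renal and hepatic values are named as pharmacokinetic covariates, not as a safety endpoint. And nothing here touches the efficacy analysis, any hypothesis test, eligibility or clinical management. This is a cheap improvement worth making, not a flaw in the trial's conclusions.

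**What to change.** In SAP 14.5, and to match in protocol 8.2.6.2, keep the low-normal-high table and add a supplementary table for ALT, AST, ALP and total bilirubin:

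- A full cross-tabulation of baseline against post-dose band in pre-specified multiples of ULN, for example <=1, >1-3, >3-5, >5-10 and >10, stating which post-dose value is used.
- The number and percent of patients whose post-dose value exceeds 3x ULN and lies in a higher band than their own baseline. A simple count of patients moving up one band would not do, because it would still count 0.95x to 1.05x ULN.
- The number and percent reaching a multiple of their own baseline, for example >=2x and >=3x, so that a rise within a band such as 1.1x to 3x ULN is not missed. Show this by baseline band, since a doubling within the normal range would also qualify.

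The bands should be fixed before database freeze so that thresholds are not chosen after the data are seen. The table uses values and normal ranges already needed for the planned table. The cost is SAP and table-shell wording, some extra rows, and counts that may look less favourable than the present table.

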5.5.4 Study Drug Administration

OTL38 will be prepared following the Dose Preparation for OTL38 Injection Pharmacy Manual (see [Appendix 1](#)). OTL38 will be administered intravenously over approximately 60 minutes. The infusion will be completed at least one hour prior to intraoperative imaging.

[REDACTED]

[REDACTED]

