6.5 Pharmacokinetics

- Primary plasma pharmacokinetic (PK) parameters for OTL38, including systemic clearance (CL), volume of distribution of the central and peripheral compartments (V_c , V_p), and distributional clearance(s) (CL_d), on a population and individual patient level.
- Effects of patient specific covariates (e.g. baseline demographics and laboratory value indicators of renal and hepatic function) upon PK parameters, reported as coefficients demonstrating significance at the alpha level of 0.05.

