8.2.6.3 Pharmacokinetics

The pharmacokinetics of OTL38 will be estimated by fitting compartmental pharmacokinetic models to the serial plasma concentration-time (Ct) data using established methods including maximum likelihood parameter estimation and nonlinear mixed-effects (NLME) modeling approaches, with the patient serving as the random effect. Various structural PK and error models will be fit to data using a qualified, standard software package. Primary PK parameters will be estimated at the population level and for individual patients as post-hoc empirical Bayesian estimates (EBEs). The actual primary parameters may vary depending on the supported model, but are likely to include systemic clearance (CL), volumes of distribution of the central and peripheral compartment(s) (V_c , V_p), distributional clearance (CL_d), or derivatives thereof. Inter-patient variability in select PK parameters will be assessed as part of the model, as will the residual error. Secondary parameters may include, but are not limited to: model predicted maximum concentration (C_{max}), time of C_{max} (T_{max}), area under the concentration-time curve (AUC) to the last time point (AUC_{last}) and to infinity (AUC_{inf}), and the terminal elimination half-

life ($T_{1/2}$). The model predicted Ct profiles and observed Ct data will be presented as figures for the population and individual level. Individual primary EBE and secondary parameters will be presented as listings at the patient level.

Potential covariates explaining inter-subject PK variability, and their influence upon PK parameters, will be initially screened using a two-stage approach with standard parametric statistical tests on the individual patient EBEs, focusing on CL. Covariates of interest will include baseline demographic values (e.g. height, weight, age, BSA, BMI, race), and laboratory values predictive of renal or hepatic function (e.g. BUN, creatinine, calculated creatinine clearance or GFR, AST, ALT, alkaline phosphatase, albumin, and total bilirubin). If warranted, a single stage approach with direct incorporation of covariates into the NLME PK model may be undertaken using a forward addition - backward deletion method at an alpha level of 0.05.

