12.5 Pharmacokinetic Endpoints

- Primary plasma pharmacokinetic (PK) parameters for OTL38, including systemic clearance (CL), volume of distribution of the central and peripheral compartments (V_c , V_p), and distributional clearance(s) (CL_d), on a population and individual patient level.
- Effects of patient specific covariates (e.g. baseline demographics and laboratory value indicators of renal and hepatic function) upon PK parameters, reported as coefficients demonstrating significance at the alpha level of 0.05.

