13.3.5 Pharmacokinetics

The pharmacokinetics (PK) of OTL38 will be estimated by fitting compartmental pharmacokinetic models to the serial plasma concentration-time (Ct) data using established methods including maximum likelihood parameter estimation and nonlinear mixed-effects (NLME) modeling approaches, with the patient serving as the random effect. Various structural PK and error models will be fit to data using a qualified, standard software package. Primary PK parameters will be estimated at the population level and for individual patients as post-hoc empirical Bayesian estimates (EBEs). The actual primary parameters may vary depending on the supported model, but are likely to include systemic clearance (CL), volumes of distribution of the central and peripheral compartment(s) (V_c , V_p), distributional clearance (CL_d), or derivatives thereof. Inter-patient variability in select PK parameters will be assessed as part of the model, as will the residual error. Secondary parameters may include, but are not limited to: model predicted maximum concentration (C_{max}), time of C_{max} (T_{max}), area under the concentration-time curve (AUC) to the last time point (AUC_{last}) and to infinity (AUC_{inf}), and the terminal elimination half-life ($T_{1/2}$). The model predicted Ct profiles and observed Ct data will be presented as figures for the population and individual level. Individual primary EBE and secondary parameters will be presented as listings at the patient level.

Potential covariates explaining inter-subject PK variability, and their influence upon PK parameters, will be initially screened using a two-stage approach with standard parametric statistical tests on the individual patient EBEs, focusing on CL. Covariates of interest will include baseline demographic values (e.g. height, weight, age, BSA, BMI, race), and laboratory values predictive of renal or hepatic function (e.g. BUN, creatinine, calculated creatinine clearance or GFR, AST, ALT, alkaline phosphatase, albumin, and total bilirubin). If warranted, a single stage approach with direct incorporation of covariates into the NLME PK model may be undertaken using a forward addition - backward deletion method at an alpha level of 0.05.

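### Covariate effects on clearance should be tabulated with 95% CIs whatever their p-value; the two-compartment PK endpoints should also be made conditional on the supported model

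*Protocol*

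**What the plan says.** Covariates. The Protocol Synopsis (Study Endpoints) lists "Effects of patient specific covariates (e.g. baseline demographics and laboratory value indicators of renal and hepatic function) upon PK parameters" and stops there. Protocol 6.5 and SAP 12.5 carry the same endpoint but add "reported as coefficients demonstrating significance at the alpha level of 0.05". SAP 13.3.5 says that covariates "will be initially screened using a two-stage approach with standard parametric statistical tests on the individual patient EBEs, focusing on CL", EBEs being the individual empirical Bayes estimates. It adds: "If warranted, a single stage approach with direct incorporation of covariates into the NLME PK model may be undertaken". Protocol 8.2.6.3 and SAP 13.3.5 then tabulate coefficients, standard errors and P values with a restriction to significance at 0.05. They also plan covariate plots, patient-level listings of EBEs, and final-model estimates with standard errors or confidence intervals.

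Structural parameters. Protocol 6.5 and SAP 12.5 name CL, the central and peripheral volumes (Vc, Vp) and distributional clearance (CLd) "on a population and individual patient level", without condition. The methods text in Protocol 8.2.6.3, repeated in SAP 13.3.5, does add one: "The actual primary parameters may vary depending on the supported model". Terminal half-life and AUCinf are possible secondary parameters.

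Sampling. The Synopsis (Assessments) has blood "drawn from all subjects at sparse time points (30, 60 and 90 minutes) following the start of OTL38 infusion". Protocol 5.5.4 says "OTL38 will be administered intravenously over approximately 60 minutes". The visible draws are therefore mid-infusion, end of infusion and about 30 minutes afterwards.

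**The concern.** A rule that reports a coefficient only when it is significant has two effects. An effect that misses 0.05 need have no number, so a reader cannot separate absence of an effect from inability to measure one. Effects that pass are overstated on average, because passing is easier when chance pushes the estimate up. For an imaging agent, renal and hepatic effects on CL are what a later reader of the PK results will look for, and the endpoint text is stricter than the Synopsis.

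The second issue is structural. Four parameters are named as endpoints for the population and for each patient, while the only visible schedule has three times common to everyone. If no other data enter the model, part of what is reported would come from the model and not from the samples.

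**Working it through.** **1. The reporting rule, side by side.** Synopsis: effects, no filter. Protocol 6.5 and SAP 12.5: coefficients significant at 0.05. Protocol 8.2.6.3 and SAP 13.3.5: the words on significance may restrict the whole row or only the P values. On the first reading, a non-significant renal or hepatic coefficient has no promised estimate or CI. Plots and EBE listings remain.

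**2. What the filter does.** Let the estimate divided by its standard error be normal with mean δ and variance 1, tested two-sided at 0.05 (c = 1.96). The mean among significant results, relative to the true mean, is 1 + [φ(c−δ) − φ(c+δ)] / (power × δ).
- Power 90%, δ = 3.24: 1 + 0.1755/(0.90 × 3.24) = 1.06.
- Power 50%, δ = 1.96: 1 + 0.3988/(0.50 × 1.96) = 1.41.
- Power 20%, δ = 1.12: 1 + 0.2765/(0.201 × 1.12) = 2.23.

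**3. Is a missed effect plausible?** No PK power is published, so there is no figure to reproduce. N = 100 is borrowed from the efficacy minimum in the Synopsis; the PK set in Protocol 8.2.2 may be larger. All effects and variances here are assumptions.
- CL known exactly, and 20% lower in 20 of 100 patients: the shift is |ln 0.8| = 0.223 and the SE is SD × √(1/80 + 1/20) = 0.25 × SD. Power is 84.5%, 60.7% and 43.1% at between-patient SDs of 30%, 40% and 50%.
- EBE screen, CL 25% lower in half the patients, SD 30%, residual error 15–20%, one compartment: power is 87–99% at half-lives of 0.5–1 h, 58–85% at 1.5 h, 37–61% at 2 h and 19–34% at 3 h. CL shrinkage is 9–26%, 28–45%, 42–59% and 61–74%. The single-stage test is no better (33–57% at 2 h, 17–30% at 3 h).
- Same effect, two compartments with typical values known: 88–99%.

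**4. Identifiability from the visible draws alone.** Put k10 = CL/Vc, k12 = CLd/Vc and k21 = CLd/Vp. Let α and β be the roots of s² − (k10 + k12 + k21)s + k10·k21 = 0, with A = (α−k21)/[(α−β)Vc] and B = (k21−β)/[(α−β)Vc]. For infusion rate R up to T = 1 h, C(t) = R[A·f(α) + B·f(β)], with f(λ) = (1−e^(−λt))/λ during the infusion and (e^(−λ(t−T)) − e^(−λt))/λ after it. Half-life is ln 2/β and AUCinf is dose/CL. Dose is 0.025 mg/kg (Synopsis) × 70 kg (assumed) = 1.75 mg.

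| CL, Vc, CLd, Vp (L/h, L, L/h, L; assumed) | 30 / 60 / 90 min, ng/mL | Half-life, h | AUCinf, ng·h/mL |
|---|---|---|---|
| 10, 8, 10, 15 | 64.38 / 88.97 / 38.49 | 2.4 | 175 |
| 5, 8.09, 14.52, 40.81 | 64.39 / 88.98 / 38.49 | 8.5 | 350 |
| 12.5, 7.81, 8.52, 7.11 | 64.39 / 88.98 / 38.49 | 1.2 | 140 |

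The concentrations agree within 0.02%, which is rounding of the parameters. Three times give a sensitivity matrix of rank 3 for four parameters, whatever N or the error. Covariate size inherits the ambiguity. The draws inform the absolute change in CL, so a drop of 2.5 L/h is 25% of 10, 50% of 5 and 20% of 12.5.

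**5. Population precision.** A mixed-effects fit also draws information from the variances and from scatter in draw times. With J the sensitivities of log concentration to the log parameters, V = JΩJ′ + σ²I, Ω = 0.09·I, σ² = 0.0225 or 0.04 (treated as known) and N = 100, the relative standard error (RSE) is the root diagonal of the inverse of N times the first-order information, variance terms included.

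| Assumed half-life | CL RSE, exact times | CL RSE, 10-min scatter | Vp RSE, exact times | Vp RSE, 10-min scatter |
|---|---|---|---|---|
| 1.9–2.9 h (3 sets) | 564–1424% | about 100–370% | 1891–3039% | about 400–790% |
| 1.6 h | 347–484% | about 65–90% | 1526–2132% | about 320–390% |
| 0.8 h | 193–269% | about 11–14% | 1834–2564% | about 100–130% |
| 0.6–0.7 h (2 sets) | 35–61% | about 8–12% | 176–412% | about 50–70% |

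The sets, as (CL, Vc, CLd, Vp), are (10,8,10,15), (15,8,10,15), (6,6,8,12); (25,10,15,20); (20,5,6,5); (30,8,10,6), (25,8,15,8). Scatter columns vary somewhat with the random times drawn. At half-lives of 0.6–0.8 h, CLd is poor at exact times but about 13–29% with 10-min scatter. RSE scales with 1/√N. In the 1.9–2.9 h sets, fixing CLd and Vp from outside data brings CL RSE to 3.3–4.2%.

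**The case against.** Much can be said for the plan. The methods text already lets the parameter list follow the supported model, and terminal half-life and AUCinf are only possible outputs. Final-model standard errors or CIs are planned, so a hopeless CL would show itself, and EBE listings and covariate plots are not filtered. The restriction in the methods text may apply to P values alone. The Visit 2 draw times (Protocol 5.7.1.2) are redacted, the Schedule of Procedures is not in the supplied text, and the PK analysis plan is not supplied. Later draws or data from earlier studies may therefore exist. PK is exploratory.

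All of this stands, and it rules out several stronger readings. A reader might infer that CL and CLd will be set by modelling choices. That follows only for slower kinetics, and the documents show no plasma half-life. Protocol 3.2 speaks of folate leaving healthy tissue within 2–3 h. If that meant 75–90% gone and applied to plasma, the half-life would be 0.6 h (90% in 2 h) to 1.5 h (75% in 3 h), mostly the faster part of the range. A reader might infer that the EBE screen is generally weak. In the cases run with a 25% drop in half the patients, it is weak mainly under one compartment at about 2 h or more. A reader might infer that the sampling needs redesign. With the draw times redacted, nothing supports that.

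None of it removes the filter in Protocol 6.5 and SAP 12.5. Plots and listings do not give a coefficient with an interval.

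**Conclusion.** This is a cheap improvement to an exploratory analysis, and it leaves the efficacy conclusions untouched. The firm part is textual: two endpoint sections report covariate effects only if significant, the Synopsis does not, and the methods text is ambiguous. The consequence is missing numbers for missed effects, and average overstatement of reported ones by a factor of about 1.06 at 90% power, 1.41 at 50% and 2.23 at 20%. The secondary part is also firm, but limited to the visible draws used alone: they do not determine four two-compartment parameters from the mean curve or in an individual. Between the endpoint and methods text this is a matter of alignment, since the condition is already written in the methods. How badly population CL would suffer is not known. It runs from unusable at assumed half-lives of 1.9–2.9 h to adequate at 0.6–0.7 h with realistic scatter in draw times. Vp stays poor, at about 50% or more, in every case run on these draws alone. All PK values, variances and effect sizes are assumptions; the rank result and the matching concentrations need no variance assumption.

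**What to change.** In Protocol 6.5 and 8.2.6.3 and in SAP 12.5 and 13.3.5, replace the significance filter with a commitment to tabulate every pre-listed renal and hepatic coefficient on CL with its 95% CI whatever its p-value, and align these sections with the Synopsis. Report CL shrinkage beside the table, and state which structural parameters were fixed and from what source. Carry the supported-model condition of the methods text into Protocol 6.5 and SAP 12.5. State that terminal half-life and AUCinf will not be reported if the 30, 60 and 90 minute draws turn out to be the only data. The cost is a few sentences and one more table, with fewer parameters claimed if the data do not support them. Power is unchanged; the interval shows how much was learned. No patients, draws or procedures are added.
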